### Protocol Abbreviations/Acronyms

Abbreviation/Acronym	Definition
AE	Adverse event
Bard	C. R. Bard, Inc.
BMI	Body Mass Index
CDC	US Centers for Disease Control and Prevention
CFR	Code of Federal Regulations
Cm	Centimeter
CT	Computed Tomography Scan
COPD	Chronic Obstructive Pulmonary Disease
CST	Component Separation Technique
CV	Curriculum vitae
eCRF	Electronic Case Report Form
e.g.	For Example
FDA	Food and Drug Administration
HIPAA	Health Insurance Portability and Accountability Act
HIV	Human Immunodeficiency Virus
Hrs	Hours
ICF	Informed Consent Form
i.e.	That Is
IRB	Institutional Review Board
IFU	Instructions For Use
LTF	Lost to Follow-Up
Mm	Millimeter
MRI	Magnetic Resonance Imaging
N	Sample Size
P4HB	poly-4-hydroxybutyrate
PE	Physical Exam
SAE	Serious Adverse Event
SF-12®	12-Item Short Form
SSI	Surgical Site Infection
VAC	Vacuum Assisted Closure system
VAS	Visual Analogue Scale

## 1 INTRODUCTION

### 1.1 Background

With more than 2 million abdominal operations occurring annually in the United States (US) and up to 20% of those patients developing ventral incisional hernias, abdominal wall defects and incisional hernias represent a challenging surgical condition. Approximately 250,000 ventral hernia repairs are performed on a yearly basis. There are several options for repair, including primary repair, mesh reinforcements, repair with relaxing incisions, and use of musculofascial flaps, utilizing both open and laparoscopic approaches. However, there is no clear-cut consensus regarding the optimal hernia repair technique, particularly in complex hernia repair cases where patient co-morbidities exist and a high risk of infection is present.

Simple suture repair has been associated with a high risk of hernia recurrence, with reports ranging from 10% to 55%, and has been nearly abandoned for the repair of hernias which are greater than five centimeters (cm) in size. As a result, many ventral hernia repair procedures involve the use of a mesh material as a soft tissue reinforcement.

Synthetic mesh repair procedures, either open or laparoscopic, have been reported to lead to fewer recurrences compared to primary repairs. Improved outcomes are believed to be related to reduced tension on the fascial edges and sutures when mesh is used in hernia repair procedures. However, complex cases and large abdominal wall defects continue to pose a challenge to surgeons. Factors such as patient co-morbidities, defect size, location, tissue viability and degree of contamination are included in a surgeon's assessment and decision-making process. These large abdominal wall defects have been associated with recurrence rates of up to 46%.

Despite the positive clinical impact of reducing hernia recurrence rates, the use of synthetic mesh has been associated with complications such as infection, adhesions, fistulae, and foreign body reactions including increased inflammation.

Non-absorbable meshes can lead to complications related to the body's reaction to the persistent foreign mesh material resulting in foreign body sensations including discomfort and chronic pain, which is described by the International Association for the Study of Pain as pain lasting for 3 months or greater following hernia repair.

Ideally, an absorbable mesh would provide adequate structural support throughout the healing process and would be fully absorbed when the wound has completely healed, thereby potentially reducing the chances for complications associated with the persistence of non-absorbable mesh material. The development of absorbable mesh products has faced challenges related to the rate of absorption with complications arising when the mesh product is absorbed too quickly. An absorbable mesh should retain its functional strength for a sufficient period of time to allow native cellular ingrowth tissue remodeling, maturation of collagen, and gradual shift of mechanical load.

Phasix™ Mesh is a commercially available medical device in the United States. It is a resorbable mesh prepared from poly-4-hydroxybutyrate (P4HB) which has been studied for use as a biomaterial for a number of applications in medical devices and tissue engineering due to favorable mechanical properties, biocompatibility and desirable degradation times. Using standard measures of mechanical strength (suture pull-out, tear and ball burst strength) Phasix™ Mesh is comparable in performance to traditional polypropylene mesh. Pre-clinical implantation studies indicate that the resorption of the Phasix™ Mesh fibers is minimal throughout the 12 week expected period of healing and up to ~26 weeks post-implantation. Resorption of the fibers is essentially complete in 12-18 months.

A bridging hernia repair study in a porcine model demonstrated that Phasix™ Mesh could perform as a durable scaffold for soft tissue repair when spanning a surgical defect. The results of the 52-week study showed that the repair site had three times greater mechanical repair strength, as compared to native abdominal wall. This persisted even after significant Phasix™ Mesh resorption (as measured by molecular weight). Only 10% of the strength of the repair site came from the Phasix™ Mesh at the 52 week timepoint. Phasix™ Mesh showed an initial mild-moderate host inflammatory response, that declined to mild over 52 weeks. Neovascularization (angiogenesis) and new collagen deposition were evident at 6, 12, 26 and 52 weeks, as histologically evaluated by a board-certified veterinary pathologist. In a 24-week rat study, histological analyses of the repair site demonstrated that some competitive meshes had a greater overall host inflammatory response, some had less of a response and one had a very similar response, to Phasix™ Mesh. In the same study, histological analyses demonstrated similar variability on measures of host fibrotic response.

This post-approval clinical study is being conducted to evaluate the use of Phasix™ Mesh in primary ventral or incisional hernia repair. Patients who receive a Phasix™ Mesh implant will be followed for 24 months.

## 1.2 Rationale

This study is intended to evaluate the use of Phasix™ Mesh for primary ventral, incisional and first-recurrent incisional hernia repair.

## 1.3 Device Descriptions

### 1.3.1 Phasix™ Mesh

The Phasix™ Mesh (Davol, Inc.) is a resorbable mesh prepared from P4HB. P4HB is produced from a naturally occurring monomer and is processed into monofilament fibers and knitted into a surgical mesh. Phasix™ Mesh degrades through a process of hydrolysis and a hydrolytic enzymatic digestive process. It was developed to minimize the variability of resorption rate (loss of mass) and strength and provide support throughout the expected period of healing.

Pre-clinical implantation studies indicate that the resorption of the Phasix™ fibers is minimal throughout the 12-week expected period of healing and up to about 26 weeks post implantation. Resorption of the fibers is essentially complete in 12 to 18 months.

Phasix™ Mesh has been commercially available in the United States since 2012 and is indicated to reinforce soft tissue where weakness exists, such as the repair of hernia or other fascial defects that require reinforcement or bridging material to obtain the desired surgical result. Because Phasix™ Mesh is fully resorbable, it should not be used in repairs where permanent wound or organ support from the mesh is required. A full description of Phasix™ Mesh is included in the product's Instructions for Use (IFU) (Appendix 2).

## 2 STUDY OBJECTIVES

The objective of this single-arm observational study is to collect additional data on safety, performance, and effectiveness of Phasix™ Mesh in subjects requiring primary ventral or incisional hernia repair.

## 3 STUDY ENDPOINTS

### 3.1 Primary Endpoint:

#### Hernia Recurrence Rate

Hernia recurrence rates will be assessed by physical examination at each study visit through 24 months. A recurrent hernia will be defined as any hernia identified or confirmed by the investigator, during any study follow-up visit, in approximately the

same position as the hernia repaired in the study procedure. Potential hernias identified via incidental magnetic resonance imaging (MRI) or computed tomography (CT) scan will be evaluated by the operating surgeon for clinical significance and confirmation of hernia recurrence.

### 3.2 Secondary Endpoints:

1. Device related adverse event incidence
2. Quality of life assessments (Carolinas Comfort Scale® and SF-12® - 12-item short form health survey)
3. Surgical procedure time as measured from incision to closure (skin to skin)
4. Length of hospital stay post index surgical procedure
5. Number of study-related post-operative surgical procedures and admissions
6. Number of study-related post-operative visits unrelated to standard of care.
7. Incidence of Seroma.

## 4 STUDY DESIGN

This is a prospective, multi-center, single-arm, observational study designed to collect additional data on safety, performance and effectiveness of Phasix™ Mesh for primary ventral or incisional or first-recurrent hernia repair. Follow-up visits will be conducted at 1, 3, 6, 12, 18, and 24 months following surgery. See Section 6 for a detailed schedule of study visits and procedures.

## 5 STUDY POPULATION

### 5.1 Number Of Subjects

This study is projected to enroll up to 30 subjects at approximately 5 US sites.

### 5.2 Eligibility Criteria

#### 5.2.1 Inclusion Criteria

The subject must meet all of the criteria listed below to be enrolled in the study:

1. Subject must be 18 years of age or older
2. Subject or subject's legally authorized representative must be willing to give written informed consent
3. Subject must be diagnosed with ventral or incisional hernia
4. Subject must be willing to undergo open ventral hernia repair and be able to undergo all other study procedures as outlined in this protocol.

### 5.2.2 Exclusion Criteria

The subject must be excluded from study enrollment if any of the following criteria are met:

#### Screening Exclusion Criteria:

1. Subject is an active smoker (if attempts to quit smoking within two weeks of surgery have failed and the patient is still an active smoker at the time of surgery).
2. Subject has had 4 or more previous hernia repairs.
3. Subject's body mass index (BMI)  $>40 \text{ kg/m}^2$ .
4. Subject has peritonitis.
5. Subject is on or suspected to be placed on chemotherapy medications during any part of the study.
6. Chronic steroid use or immunosuppression drugs ( $> 6$  months).
7. Subject has cirrhosis, and/or ascites.
8. Subject is American Society of Anesthesiology Class 4 or 5.
9. Subject is pregnant or planning to become pregnant during the course of the study.
10. Subject is known to be infected with human immunodeficiency virus (HIV).
11. Subject has a life expectancy of less than 2 years at the time of enrollment.
12. Subject has been treated with an investigational product in the past 30 days.
13. Subject is part of the site personnel directly involved with this study
14. Subject has a known allergy to tetracycline hydrochloride or kanamycin sulfate, the test device or its component materials.
15. Subject has any condition that in the opinion of the Investigator would preclude the use of the study device, or preclude the subject from completing the follow-up requirements.

#### Intra-operative Exclusion Criteria:

16. The fascia cannot be closed intraoperatively.
17. The use of surgical repair as a bridge.
18. Patient has a contraindication to placement of mesh.
19. Complete removal of existing mesh from a prior hernia repair (in the same affected area) is not possible.
20. Skin closure cannot be achieved intraoperatively.
21. Subject has an active or latent systemic infection

## 6 STUDY PROCEDURES

### 6.1 Subject Screening and Baseline Evaluation

Subjects with a diagnosis of a primary ventral or incisional hernia or up to 3 recurrent hernias requiring surgical repair to close the defect will be screened for potential eligibility against the study protocol inclusion and exclusion criteria, utilizing ordinary standard of care procedures (e.g. physical examination, blood work, medical evaluation) within 60 days of the date of consent. This may include a full anesthetic work-up customary for hernia repair procedures. Any other standard of care examination or evaluation within 60 days of the date

of consent may be considered baseline for study purposes. Prior medical records documenting these tests, examinations and evaluations may be used as the source documents for the baseline visit.

During the screening and recruitment process, the Investigator will be responsible for describing the nature of the clinical study, verifying that the eligibility criteria have been met, and obtaining informed consent. Written informed consent and a Health Insurance Portability and Accountability Act (HIPAA) waiver must be obtained prior to performance of any protocol specific procedures.

The following screening/baseline procedures will be conducted and documented.

#### 6.1.1 Informed Consent

The investigator will explain the study to the subject, answer all of the subject's questions, and obtain written informed consent in a language in which the subject is fluent before the collection of any study data or performance of any study procedures.

The subject (or subject's legally authorized representative) must be willing and able to sign and date the informed consent form (ICF) prior to the collection of study data or performance of any study procedures. The original, signed informed consent will be retained with the subjects' records and a copy provided to the subject.

#### 6.1.2 Enrollment

Subjects who sign the informed consent and receive Phasix™ Mesh as a part of this study will be considered enrolled in the study.

#### 6.1.3 Eligibility

The subject's eligibility for study enrollment will be reviewed and documented on the appropriate eCRF. At the time of screening, a related progress note must be entered in the source documentation to indicate that all eligibility criteria were reviewed and screening results noted. Final eligibility will be determined intraoperatively.

Subjects who fail to meet eligibility criteria should be considered screen failures and treated according to the Investigator's standard of care. Data are to be collected for screen failure subjects from the time the ICF is signed until the subject is deemed a failure. At a minimum, subject demographics and the reason for failure must be collected; adverse events (AEs) will also be collected and followed through satisfactory resolution or stabilization.

#### 6.1.4 Assignment of Subject Screening Number

A unique identification number will be given to study subjects. Subject numbers will be assigned in a sequential order. The subject number will consist of six digits. The first three digits will designate the study site. The last three digits will designate the subject by number in sequential order at each study site.

#### 6.1.5 Blinding

The study is an open-label study with a single treatment condition. Subjects and investigator (and surgeon) will be not be blinded to the study treatment.

#### 6.1.6 Demographics and Medical History

The subject's medical history and demographic information will be documented on the appropriate eCRF. Demographic information will include gender, date of birth, race and ethnicity.

#### 6.1.7 Physical Examination

A standard physical exam, appropriate to subjects about to undergo abdominal surgery, will be performed by the physician. Height and weight measurements will be recorded to allow for the calculation of BMI. The subject's ability to participate and meet the follow-up requirements will be established.

#### 6.1.8 Concomitant Pain Medication Usage

Prescription and over the counter (OTC) pain medication must be recorded in the source documentation and in the eCRF. The condition/s necessitating the pain medication will be recorded. All current pain medication will be captured at baseline, 12 months, and 24 months.

#### 6.1.9 Patient Reported Outcome Assessments

Subjects will complete the Carolinas Comfort Scale® and SF-12® to measure discomfort and quality of life.

### 6.2 Surgical Procedure

#### 6.2.1 General Procedures

All subjects will undergo an open ventral repair of hernias. All intraoperative eligibility criteria should be verified. Defect closure, defined as both fascial and skin closure, must be confirmed.

The surgical technique will require retro-rectus or onlay placement (using absorbable suture) with or without Component Separation Technique (CST). Subjects will be administered antibiotics according to hospital protocol.

Subjects are prepared to undergo hernia repair following the instructions supplied by the Sponsor. The IFU for Phasix™ Mesh device is presented in Appendix 2.

Phasix™ Mesh will be placed in the retro-rectus or onlay space with absorbable mesh fixation. The peritoneum should remain posterior to the mesh upon completion of mesh placement. Phasix™ Mesh may be cut to shape or size desired for each specific application. To prevent recurrence when repairing hernias, a mesh larger than the defect is required to ensure adequate coverage. The mesh is to be positioned so its edges extend beyond the margins of the defect by at least 5 cm. It is recommended that fixation be placed at approximately 5 to 6 cm intervals (6 to 12 resorbable sutures) around the periphery of the mesh. The edges are then fixated to assure proper closure under correct tension.

The procedure may include CST to obtain site closure. All incisions will be closed with staples and/or sutures and wounds will be dressed with sterile occlusive dressings.

### 6.2.2 Component Separation Technique Surgery

Prophylactic antibiotics will be administered according to hospital protocol. If a prior hernia repair utilizing mesh is in the affected area, complete removal of any mesh remaining is required. Once all of the dissection is performed and all of the hernia has been exposed, the largest vertical and transverse dimensions should be recorded.

If the CST is utilized, the surgical technique will be a modification of the “component separation technique” by Ramirez et al. with the graft being implanted into the tissue plane of the surgeon’s preference, according to the following: Separation of components may be done via open, posterior or endoscopic/minimally invasive technique as described below.

#### 6.2.2.1 Open Technique

After entering the abdominal cavity, adhesiolysis is performed to dissect free any intra-abdominal contents from the abdominal wall. The skin and subcutaneous fat are dissected free from the anterior sheath of the rectus abdominal muscle and the external oblique muscle. The external oblique is separated through the aponeurosis approximately 1-3 cm from the edge of the rectus, or through the muscle. If the hernia is subxiphoid in position, release must be done above the rib cage and come across the rectus sheath and muscle at the level of where the pectoralis meets the rectus. The external oblique muscle is separated from the internal oblique muscle, as far laterally as possible (aiming to the anterior axillary line), above and below the hernia by approximately 5 cm.

#### 6.2.2.2 Posterior Technique

Posterior component separation with transversus abdominis release (TAR): Starting in the upper third of the abdomen, about 0.5 cm medial to the anterior/posterior rectus sheath junction (linea semilunaris), the posterior rectus sheath is incised to expose the underlying transversus abdominis muscle. The muscle is then divided along its entire medial edge using electrocautery. The use of a right-angled dissector significantly facilitates this release and minimizes injury to the underlying transversalis fascia and peritoneum. Transection of the medial edge of the transversus abdominis muscle allows for entrance to the space between the transversalis fascia and the lateral edge of the divided transversus abdominis muscle. The retromuscular space is bluntly developed further laterally to as far as the lateral border of the psoas muscle to allow for a reinforcement of a visceral sac with a large mesh. Also, if needed, this dissection may be extended superiorly above the costal margin and inferiorly to expose both myopectineal orifices.

#### 6.2.2.3 Endoscopic/Minimally Invasive Technique

Make a 2 cm incision in the upper abdomen in a location that is convenient for release (such as directly over the costal margin at the level of the mid clavicular line, or at the tip of the 11th rib). Please note: this incision may occasionally need to be placed further lateral to ensure the incision is lateral to the linea semilunaris. Dissect down to the level of the external oblique muscle. Separate the external oblique muscular fibers (this allows for visualization of the underlying internal oblique aponeurosis below). Advance a balloon dissector between the internal and external oblique muscle down to the level of the inguinal ligament. Insufflate the balloon under endoscopic visualization. Remove the dissecting balloon and replace with a trocar (first port). Infuse the lateral abdominal cavity with gas, such as carbon dioxide. Place a second port into the lateral abdominal cavity to allow for dissection. A third port may be used to facilitate easier access to parts of the anatomy. If performing a minimally invasive technique multiple incisions may be used to visualize and release the external oblique under direct visualization. Use cautery or alternatively ultrasonic dissection to divide the external oblique muscle from the costal margin down to the inguinal ligament. Please note: extending the dissection to the level of Scarpa's fascia results in even greater abdominal wall advancement. This technique is generally performed bilaterally.

#### 6.2.2.4 Open or Endoscopic Technique

If necessary, resect/debride the edges of the rectus fascia to ensure apposition of healthy well-vascularized tissue as the midline is closed. Care must be taken not to damage the blood supply and the nerves that run between the internal oblique and transverse muscle and enter the rectus abdominal muscle at the posterior side.

Closure should be performed with permanent or long lasting sutures every 1-2 cm between sutures, for example with an interrupted Figure-8 closure or running stitch. The surgeon should make every effort to close the fascial edges including the use of the component separation technique. If the fascia cannot be closed, the peritoneum of the hernia sac should

have been preserved so that this can be closed over the Phasix™ to provide vascularized tissue.

If a previous scar of skin is present, the scar should be excised. The fascial and subcutaneous layer should be closed with sutures. The skin should be closed with staples and/or sutures. When skin closure can't be achieved, a wound vac can be used.

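### Section 6.3.1 makes a subject who already carries Phasix Mesh a screen failure if closure then fails, against the plan's own enrolment, follow-up and mITT rules (minor)

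*Protocol*

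**What the plan says.** **Rules that take the subject out.** Protocol 5.2.2 opens with "The subject must be excluded from study enrollment if any of the following criteria are met". Its intra-operative list includes "The fascia cannot be closed intraoperatively" (criterion 16), bridged repair (17) and "Skin closure cannot be achieved intraoperatively" (20). Section 6.2.1 adds: "Defect closure, defined as both fascial and skin closure, must be confirmed". Section 6.1.3 settles final eligibility during surgery and ends data collection for a screen failure once the failure is declared. Section 6.3.1 gives two separate routes to screen failure: no device placed, or an intra-operative criterion not met. Either one leads to hospital standard of care, with follow-up of adverse events only.

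**Rules that keep the subject in.** The end of Protocol 1.1 says, without qualification, that patients who receive the implant are followed for 24 months. Section 6.1.2 treats a consented subject who receives the mesh as part of the study as enrolled. Protocol 7.3 and SAP Section 4 define mITT as ITT plus implantation, with no condition on closure or eligibility. Section 6.3.2 gives the full schedule to those successfully implanted, a term that is not defined.

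**The surgical text.** One sentence of Section 6.2.2.4 begins "If the fascia cannot be closed, the peritoneum of the hernia sac should". The instruction for that layer, which shows that the mesh stays in, is that it should "have been preserved so that this can be closed over the Phasix™ to provide vascularized tissue". For skin the section says "When skin closure can't be achieved, a wound vac can be used"; that sentence does not mention the mesh. Both sentences fall under component separation, which is optional: "If the CST is utilized, the surgical technique will be a modification of the".

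**The concern.** A subject can have the mesh in place before closure fails. Skin is the most plausible case, because it is closed after retro-rectus or onlay placement. For fascia, Section 6.2.2.4 describes the situation outright, although criteria 16 and 17 exclude it. The wound-vac sentence likewise sits uneasily with criterion 20.

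If 6.3.1 is followed as written, a treated subject leaves the study because of how the operation ended. Three things are then lost:

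- the scheduled examinations for recurrence;
- the scheduled safety visits, although the protocol puts resorption of the mesh at 12 to 18 months and Appendix 3 counts deep infection with an implant for up to one year;
- a defined place for that subject's adverse events, because the separate summary in Protocol 7.3 covers only subjects without mesh and the main analyses rest on mITT.

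Sites may also resolve the conflict differently.

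**Working it through.** **Step 1: status of an implanted subject whose fascia or skin then cannot be closed.**

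| Source | Result |
|---|---|
| Protocol 5.2.2 | excluded from enrolment |
| Protocol 6.1.3 and 6.3.1 | screen failure, adverse events only |
| SAP 7.1 | screen failures reported by criterion not met, apart from the ITT and mITT counts |
| Protocol 1.1 | followed for 24 months |
| Protocol 6.1.2 | enrolled |
| Protocol 7.3 and SAP Section 4 | in mITT, if enrolled |
| Protocol 6.3.2 | full schedule, if successfully implanted (undefined) |

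The first three rows point one way and the next three the other. No text requires eligibility to be settled before the mesh is placed, so timing does not remove the conflict. Section 6.3.1 uses the word enrolled for its screen failures, but this is probably loose usage for consented and does not decide the matter.

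The specific exclusion rules can reasonably be taken to override the general enrolment definition. Since ITT consists of enrolled subjects, the likelier result is that the subject falls outside both ITT and mITT.

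**Step 2: size on that reading.** The plan states no figure to reproduce; the sample size of 30 is expressly not statistical. The inputs are therefore:

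- 30 implanted subjects, the planned maximum (Protocol 5.1);
- one subject without closure (assumed; the documents give no number);
- 3 recurrences among the other 29 and no other losses (assumed);
- recurrence risk p for the subject without closure of 10% to 46% (assumed). The lower value is about the rate in the others. The upper value is the Protocol 1.1 figure for large abdominal wall defects, borrowed only as a bound.

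Weight of one subject: 1/30 = 3.3%.

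Expected rate if all 30 are followed = (3 + p)/30:

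- p = 0.10: 3.10/30 = 10.33%
- p = 0.46: 3.46/30 = 11.53%

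Reported rate with the subject dropped = 3/29 = 10.34% (exact 95% interval 2.2 to 27.4%).

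Shortfall = expected minus reported:

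- p = 0.10: 10.33 − 10.34 = −0.01 points
- p = 0.46: 11.53 − 10.34 = 1.19 points

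The shortfall is zero when (3 + p)/30 = 3/29, that is, when p = 3/29 = 10.3%, the rate in the rest.

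In a single realised study, keeping the subject gives 3/30 = 10.0% (exact interval 2.1 to 26.5%) without a recurrence, or 4/30 = 13.3% (3.8 to 30.7%) with one. Both estimates lie well inside the interval around 3/29.

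**The case against.** The best reply is that the documents do give an answer. Sections 5.2.2, 6.1.3 and 6.3.1 agree on screen failure, and SAP 7.1 reports such subjects separately. The sponsor chose to study closed, non-bridged repairs, which is a legitimate choice in a descriptive study with no hypothesis. The fallback text in 6.2.2.4 applies to optional component separation, after every effort to close the fascia. Deviations are already documented and listed (Protocol 12.4, SAP 7.2).

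Much of this stands, and it rules out two stronger readings that a reader might infer.

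- **That the subject would be counted as recurrence-free without being examined.** This requires the same person to be both a screen failure and an active mITT member, which the exclusion rules and SAP 7.1 do not favour. Even then, SAP Section 5 removes anyone recorded as discontinued before a visit window, so at most the earliest interval and the whole-period rate would be exposed. The available-data rates in Protocol 7.3 and Kaplan-Meier censoring would not count the subject as event-free.
- **That the recurrence rate could be badly understated.** No document suggests that two or three such subjects are to be expected, and none links failed skin closure to a 46% recurrence risk.

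The objection does not remove the conflict with Sections 1.1 and 6.1.2 and with the mITT definition. Nor does it justify ending scheduled follow-up of someone who carries the device. A restriction to closed repairs can be applied in the analysis without giving up that subject's data.

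**Conclusion.** The point holds as a minor one. The status rules conflict for an implanted subject who then fails closure, and Section 6.2.2.4 contradicts criteria 16 and 17 for fascia and criterion 20 for skin. Exclusion is the likelier reading, so the status is not wholly open. The difficulty is that exclusion drops a treated subject on a post-treatment surgical result.

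The number affected is unknown and may be zero. For one subject the understatement of recurrence is about 0 to 1.2 points on the assumptions shown. It vanishes if such subjects recur as often as the rest, and it is small beside the width of the exact interval. The more certain loss is the scheduled recurrence and safety follow-up of that subject.

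**What to change.** 1. **Protocol 6.3.1:** limit screen failure to subjects in whom the mesh was not implanted. Add that an implanted subject later found to fail criterion 16, 17 or 20 stays enrolled and in mITT, follows the full 24-month schedule, and is recorded as a protocol deviation. Put a matching exception in the opening sentence of 5.2.2.
2. **Protocol 6.2.2.4:** state that the mesh is not placed as a study device once the fascia is known not to close, and refer to 6.3.1 if fascia or skin closure fails after placement.
3. **Optional:** also report the recurrence rate without these subjects. Protocol 7.3 already allows a per-protocol set for this. The SAP does not carry that set forward, so it would need to do so and to name non-closure as a major violation.

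The cost is short wording changes in three sections and up to six scheduled visits per affected subject, with no change in sample size. It is a change of rule, because it keeps implanted subjects whom the criteria now exclude. The mITT set becomes slightly more mixed, and the reported recurrence rate may be slightly less favourable.
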